### 3.4 Efficacy Assessment

Efficacy data will be analyzed for ITT population, Per Protocol MITT population, Phage Persistence and Clearance population, and Phage-Sensitivity ITT population (if needed):

- Efficacy analysis performed using ITT population and Phase-Sensitivity ITT population (if needed) will be summarized by pooled treatment versus pooled placebo for Phase 1b and Phase 2a:
  - Phase 1b (uncomplicated SAB) vs Phase 1b placebo
  - Phase 2a (complicated SAB) vs Phase 2a placebo
- Efficacy analysis performed using Per Protocol MITT population will be summarized by pooled treatment versus pooled placebo for Phase 2a:
  - Phase 2a vs Phase 2a placebo.
- Efficacy analysis performed using Phage Persistence and Clearance population will be summarized by following:
  - Combination of Phase 1b (excluding cohort 1) and Phase 2a Persistence vs Combination of Phase 1b (excluding cohort 1) and Phase 2a Clearance vs Combination of Phase 1b placebo (excluding cohort 1) and Phase 2a placebo
  - Phase 2a Persistence vs Phase 2a Clearance vs Phase 2a placebo

Combination of Phase 1b placebo (excluding cohort 1) and Phase 2a placebo includes Phase 1b placebo (excluding cohort 1) and Phase 2a placebo in the ITT population. Phase 2a placebo includes Phase 2a placebo in the ITT population.

Phage Persistence and Phage Clearance Population and Phage-Sensitivity ITT population (if needed) will be reported by the Sponsor separately. Subject lists for Phage Persistence and Phage Clearance Population and Phage-Sensitivity ITT population (if needed) will be provided by Sponsor for analysis.

The endpoints in section 3.4.1 for Phase 1b and Phase 2a may be assessed as secondary endpoints.

### 3.4.1 Efficacy Endpoints Assessments

A National Early Warning Score 2 (NEWS2) score will be recorded once per day (and should be repeated if there is a change in clinical status) from Day 1 through Day 7 and TOC for study drug (Day 12). NEWS2 is an aggregate scoring system derived from 6 physiologic parameters: respiration rate, oxygen saturation, systolic blood pressure, pulse rate, level of consciousness or new confusion, temperature.

Table 1 per protocol section 7.4 presents the NEWS2 scoring system. NEWS2 scores will be calculated programmatically.

**Table 1. National Early Warning Score 2 Scoring System**

Physiological parameter	3	2	1	Score 0	1	2	3
Respiration rate (per minute)	≤8		9–11	12–20		21–24	≥25
SpO 2 Scale 1 (%)	≤91	92–93	94–95	≥96			
SpO 2 Scale 2 (%)	≤83	84–85	86–87	88–92 ≥93 on air	93–94 on oxygen	95–96 on oxygen	≥97 on oxygen
Air or oxygen?		Oxygen		Air			
Systolic blood pressure (mmHg)	≤90	91–100	101–110	111–219			≥220
Pulse (per minute)	≤40		41–50	51–90	91–110	111–130	≥131
Consciousness				Alert			CVPU
Temperature (°C)	≤35.0		35.1–36.0	36.1–38.0	38.1–39.0	≥39.1	

Note: **CVPU** = Confusion, Voice, Pain, Unresponsive; SpO2 = oxygen saturation. SpO2 Scale 2 (%) is meant to be used for specific population-COPD subjects with hypercapnic respiratory failure.

Time to reach a NEWS2 score ≤2 maintained for at least 24 hours or hospital discharge (whichever comes first) will be analyzed.

Time-to-event (days) = Censoring date/event date – date of first dose of study drug + 1

The Kaplan-Meier method will be used to estimate the 25%, median and 75% times. The hazard ratio, 95% confidence interval (CI) of hazard ratio, and p-value from Cox regression model will be provided to compare AP-SA02 and placebo. Cox regression will include treatment (AP-SA02 and placebo) as factor. All assessments from scheduled and unscheduled visits will be included in the time-to-event analysis. Censoring rules for the endpoint are summarized in [Table 2](#).

The Kaplan-Meier plot of time to reach a NEWS2 score  $\leq 2$  maintained for at least 24 hours or hospital discharge (whichever comes first) will be provided.

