### 2.2.4 Sample Size Determination

The study will enroll approximately 50 eligible subjects. Enrollment may be expanded up to a total of approximately 100 subjects to ensure that at least 8 treated and 4 placebo Phase 2a subjects are MRSA subjects and to account for additional subjects and cohorts that may be enrolled based on DRC review and Sponsor input based on emerging data. To ensure that at least 8 treated and 4 placebo Phase 2a subjects are MRSA subjects, no more than approximately 70 non-MRSA subjects will be enrolled without a protocol amendment.

The Phase 1b MAD safety cohorts will follow a standard 3 + 1 design for 2 cohorts (n = 4 for each cohort for a total of 8 subjects). However, additional cohorts (up to 3) may be added or existing cohorts expanded per recommendation of the DRC or Sponsor decision. The total sample size in Phase 1b may be increased up to a total of 20 subjects without a protocol amendment in consultation with the DRC.

Phase 2a will have an initial sample size of approximately n = 42 with a study drug to placebo allocation of 2:1 in order to enroll at least 38 subjects meeting the Microbiological Intent-to-Treat (MITT) Population criteria with the assumption that approximately 90% of randomized subjects will satisfy the MITT Population criteria. This will provide at least 80% power to detect a difference of 50% in the proportion of subjects in each treatment arm, with a 30% placebo portion meeting all conditions for Clinical Improvement or response at TOC for study drug (Day 12) in the MITT Population with a type 1 error rate of 0.05 (1-sided) using Fisher's exact test. Additional subjects may be included in Phase 2a after a protocol amendment.

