If Day 12 blood culture is positive, the subject will not be considered have initial resolution of SAB although there may be 2 or more consecutive negative blood cultures before Day 12. If EOS or BAT blood culture is positive, the subject will be considered as initial resolution of SAB when there are 2 or more consecutive negative blood cultures before EOS or BAT, and the initial resolution date and time will be the first date and time with 2 consecutive negative blood cultures. The subjects who do not experience the resolution will be censored at the last collection date and time of blood culture.

- Time to initial resolution of SAB (days) = (Censoring date and time/first date and time of 2 consecutive days with negative SA blood culture – date and time of first dose of study drug) /3600/24

The Kaplan-Meier method will be used to estimate the 25%, median and 75% times. The hazard ratio, 95% confidence interval (CI) of hazard ratio, and p-value from Cox regression model will be provided to compare AP-SA02 and placebo. Cox regression will include treatment (AP-SA02 and placebo) as factor.

The Kaplan-Meier plot of time to initial resolution of SAB will be provided.

Time to resolution of any signs and/or symptoms of bacteremia present at Screening will be analyzed using the Kaplan-Meier method as other time-to-event endpoints.

- Time to resolution of signs/symptoms of bacteremia (days) = Censoring date/date of first resolution of any signs/symptoms of bacteremia - date of first dose of study drug + 1

The Kaplan-Meier method will be used to estimate the 25%, median and 75% times. The hazard ratio, 95% confidence interval (CI) of hazard ratio, and p-value from Cox regression model will be provided to compare AP-SA02 and placebo. Cox regression will include treatment (AP-SA02 and placebo) as factor.

The Kaplan-Meier plot of time to resolution of any signs and/or symptoms of bacteremia present at Screening will be provided.

The signs and symptoms of SAB will be determined programmatically based on the following:

- Documented temperature  $\geq 38.0^{\circ}\text{C}$  ( $100.4^{\circ}\text{F}$ ) or  $\leq 36.0^{\circ}\text{C}$  ( $96.8^{\circ}\text{F}$ ) measured orally,  $\geq 38.5^{\circ}\text{C}$  ( $101.3^{\circ}\text{F}$ ) or  $\leq 36.5^{\circ}\text{C}$  ( $97.7^{\circ}\text{F}$ ) measured tympanically, or  $\geq 39^{\circ}\text{C}$  ( $102.2^{\circ}\text{F}$ ) or  $\leq 37^{\circ}\text{C}$  ( $98.6^{\circ}\text{F}$ ) measured rectally;

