## 7 PROGRAMMING SPECIFICATIONS

Analyses will be performed using SAS® version 9.3 or higher. Detailed Programming Specifications will be provided in a separate document.

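### SAP 3.4.1 and 3.6 name no tie method for Cox models on whole-day times; if Breslow is used, the hazard ratios for NEWS2 and for fast sign resolution are pulled toward 1

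*SAP*

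**What the plan says.** SAP 3.4.1 counts the NEWS2 time as the event or censoring date minus "date of first dose of study drug + 1", which is a whole number of days. Focal-sign resolution (SAP 3.4.1) has the same form. So does bacteremia-sign resolution (SAP 3.6), which runs to the "date of first resolution of any signs/symptoms of bacteremia". Each gets Kaplan-Meier quartiles and a Cox hazard ratio with 95% CI and p-value; the model statement is "Cox regression will include treatment (AP-SA02 and placebo) as factor".

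NEWS2 is scored once a day on Days 1 to 7 and again at Day 12, with repeats if clinical status changes. SAP Table 2 requires two consecutive days at 2 or less and dates the event to the earlier one; discharge also counts as an event. Focal signs are assessed daily on Days 1 to 7, then at Day 12, TOC for BAT and EOS.

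Neither document names a method for tied times. SAP 7 says "Analyses will be performed using SAS", version 9.3 or higher, and leaves programming detail to a separate document. Time to initial resolution of SAB (SAP 3.6) uses date and time, so it is not on the whole-day scale.

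SAP 2.2.4 plans an "initial sample size of approximately n = 42 with a study drug to placebo allocation of 2:1". The target behind that number is 38 or more MITT subjects.

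**The concern.** With about 38 subjects and a handful of possible event days, many events share a date, and the estimate then depends on how the partial likelihood treats them. The Breslow approximation keeps every subject who has an event on a given day in the risk set for all of that day's events. If one arm resolves faster, its subjects stay over-represented in those denominators and the hazard ratio shrinks toward 1. Efron's method removes tied subjects progressively and stays much closer to the result from unrounded times.

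At stake is the estimate for the first-listed Phase 2a endpoint. Two programmers following this SAP could report hazard ratios of about 2.0 and 2.4 from the same data. A choice of that consequence should not be left until results are visible.

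**Working it through.** **1. Inputs from the documents.** At 90% of 42 randomized subjects, 42 × 0.90 = 37.8, about 38. At 2:1, 38 × 2/3 = 25.3, so 25 on AP-SA02 and 13 on placebo. The documents give no hazard, hazard ratio, event count or power for any Cox analysis; those used below are assumptions.

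**2. The plan's own power figure.** SAP 2.2.4 claims "at least 80% power to detect a difference of 50% in the proportion of subjects in each treatment arm" for Day 12 clinical response: 30% on placebo, hence 80% on AP-SA02, one-sided 0.05, Fisher's exact test. Power is the sum of Bin(a; n1, 0.80) × Bin(b; n0, 0.30) over all outcomes (a, b) that Fisher's test rejects. Enumeration gives 87.8% at 25/13 and 86.3% at 26/12. The claim holds. It concerns another endpoint, which Cox ties do not touch.

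**3. Ties implied by the schedule.** Scheduled daily scores on Days 1 to 7, with the event dated to the earlier of two consecutive days, place NEWS2 events on Days 1 to 6. Protocol Section 3 expects subjects to be inpatients through Day 7, so early discharge should add few further dates.

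**4. The two likelihoods.** On a day with d events, s of them on AP-SA02, and n1 and n0 subjects at risk, write θ for the hazard ratio. The numerator is θ^s in both.
- Breslow denominator: (n1·θ + n0)^d.
- Efron denominator: the product over l = 0, …, d−1 of [(n1·θ + n0) − (l/d)(s·θ + d − s)].

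They agree when d = 1 and separate as d grows.

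**5. Benchmark without ties.** Schoenfeld with 38 events at hazard ratio 2.5, two-sided 0.05: √(38 × 0.658 × 0.342) × ln 2.5 − 1.96 = 2.92 × 0.916 − 1.96 = 0.72, so power is about 76%.

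**6. Simulation for NEWS2.** 25 vs 13 subjects, exponential times rounded up to whole days, events on Days 1 to 6 only, true hazard ratio 2.5, two-sided 5% Wald test, 1,500 runs per row, median hazard ratios:

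| Placebo median | Breslow HR, power | Efron HR, power | Points lost |
|---|---|---|---|
| 2 days | 2.01, 41% | 2.45, 66% | 25 |
| 3 days | 2.13, 48% | 2.47, 64% | 16 |
| 4 days | 2.26, 50% | 2.53, 63% | 13 |
| 5 days | 2.23, 44% | 2.44, 56% | 12 |

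At 2 days there are about 36 events on 5 distinct days, 18 of them on the busiest; unrounded times give 2.54 and 69%. A separate run of the same design gave 1.97, 39% against 2.38, 65% at 2 days, and 2.32, 48% against 2.54, 57% at 5 days. With no true effect and medians of 2 to 4 days, Breslow rejects 1.8% to 3.5% of the time and Efron 4.4% to 5.0%. At a true hazard ratio of 1.5 the loss is about 3 to 9 points.

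**7. Where ties matter little.** Breslow is given first, then Efron; true hazard ratio 2.5 except for death.
- Slow resolution, placebo daily hazard 0.05 or 0.03 over 60 days: 20 to 23 distinct event days, 4 to 5 events on the busiest; 2.43 vs 2.53 and 2.48 vs 2.53; 3 to 4 points lost.
- Discharge after Day 7 with a further median of 7 days: 2.34 vs 2.50, power 60.9% vs 66.6%. Median 14 days: 2.42 vs 2.48, 64.8% vs 67.2%. Only if discharges cluster soon after Day 7 (further median 3 days) does the loss reach 15 points (53.2% vs 68.4%).
- Death, assuming 15% or 30% placebo mortality and hazard ratio 0.4: about 3 or 7 events, at most 1 to 2 on a day; the two methods give the same result.

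**The case against.** - **The default is not in the documents.** They name SAS and nothing more, and the programming specifications could already set another method. This stands: Breslow is an assumption. But the SAP as written permits either method, and a choice that moves the hazard ratio belongs in the SAP.
- **Nothing is formally tested.** Protocol 9.2.1 and SAP 3.1.4 say so, and the only powered analysis is Day 12 response. This stands: no planned power is lost, and a conservative p-value creates no false claim of benefit. Kaplan-Meier quartiles and the daily NEWS2 proportions are unaffected. The hazard ratio and CI are still required outputs, and a descriptive phase rests on its estimates.
- **The sign endpoints may not be heavily tied.** Focal resolution needs all signs absent and is followed to EOS, so it may be slow. This stands; the problem for those endpoints is conditional on fast resolution.
- **Efron may not restore the true value.** No entry criterion requires NEWS2 above 2, and pain alone meets inclusion criterion 7, so some subjects may have the event on Day 1. If 30% or 50% do (assumed), Efron also gives only about 1.8 to 1.9 or 1.5 to 1.6 when the true hazard ratio is 2.5. This stands as a limit on what the fix achieves; Efron remains closer than Breslow.

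**Conclusion.** The point holds for NEWS2, and for focal-sign and bacteremia-sign resolution if they resolve fast. If Breslow is applied, a true hazard ratio of 2.5 is reported as about 2.0 rather than about 2.4 at a placebo median of 2 days, with about 25 points of power lost. At 5 days it is about 2.3 rather than 2.5, with about 10 points lost. These sizes rest on exponential times, a 25:13 split and assumed medians and hazard ratio.

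A reader might infer that every whole-day Cox analysis here is badly distorted, or that the trial gives up a quarter of its power. The documents support neither. Time to death is unaffected, and late discharge or slow resolution loses about 2 to 6 points. The loss found across assumed settings runs from 0 to about 44 points (the extreme at a placebo median of 1 day), so a quarter is no bound, and no Cox analysis has a planned power to lose. The main harm is an estimate biased toward no effect.

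**What to change.** State in SAP 3.4.1 and 3.6, before database lock, that the whole-day Cox models use TIES=EFRON, with exact or discrete ties as a sensitivity analysis for NEWS2 and sign/symptom resolution. If the discrete method is chosen, label its result separately: it estimates an odds ratio and runs higher. With a placebo median of 5 days, daily assessment and 12-day follow-up, it gave 2.81 for a true hazard ratio of 2.5, against 2.49 for Efron. Carry the same option into the programming specifications.

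The cost is one sentence and one model option, with no new data and no protocol amendment. Models with few ties, such as time to death, will not change.

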**Table 2. Time-to-event Endpoint**

Endpoint: time to reach a NEWS2 score <math>\leq 2</math> maintained for at least 24 hours or hospital discharge		
Situation	Date of event or censoring	Outcome
NEWS2 score $\leq 2$ maintained consecutive 2 days while hospitalized	Earlier date of these two consecutive 2 days	Event
Hospital discharge (i.e., Discharge to home, transferred to long term acute care – LTAC, transferred to long term care facility – LTCF) and no NEWS2 score $\leq 2$ maintained consecutive 2 days while hospitalized	Date of hospital discharge	Event
No occurrence of hospital discharge to home and no NEWS2 score $\leq 2$ maintained consecutive 2 days	Date of last visit	Censored

In [Table 2](#), the hospital discharge types include discharge to home, transferred to long term acute care – LTAC, and transferred to long term care facility – LTCF.

Proportion of subjects reaching a NEWS2 score  $\leq 2$  maintained for at least 24 hours or hospital discharge (whichever comes first) at Day 2, Day 3, Day 4, Day 5, Day 7, and TOC for study drug (Day 12) will be analyzed. The hospital discharge types include discharge home, transferred to long term acute care – LTAC, and transferred to long term care facility – LTCF. The responders will be subjects reaching a NEWS2 score  $\leq 2$  maintained for at least 24 hours or hospital discharge. Proportion of responders will be provided. Chi-square test p-value will be provided to compare AP-SA02 and placebo.

The proportion of subjects reaching a NEWS score  $\leq 2$  maintained for at least 24 hours or hospital discharge (whichever comes first) will be plotted by AP-SA02 and placebo at Day 2, Day 3, Day 4, Day 5, Day 7, and TOC for study drug (Day 12).

NEWS2 score while hospitalized will be summarized with descriptive statistics by study day and changes from baseline for each study day will be summarized. A paired t-test p-value will be used to compare the baseline value with each scheduled post-baseline values. An unpaired t-test p-value will be used for the change from baseline at each scheduled study day to compare AP-SA02 and placebo.

NEWS2 score while hospitalized and changes from baseline will be plotted by AP-SA02 and placebo at each scheduled study day for each subject.

Clinical improvement or response (meets all criteria on [Table 2](#) in [section 7.3 of protocol](#)) at TOC for study drug (Day 12), TOC for BAT (7 days  $\pm 1$  day] after the end of BAT) and EOS (28 days after the end of BAT) will be assessed by both investigator and Clinical Efficacy Adjudication Committee (CEAC).

Based on both investigator and CEAC assessments, proportion of subjects who experience clinical improvement or response will be provided. Chi-square test p-value will be provided for clinical improvement or response to compare AP-SA02 and placebo.

The proportions of responders (including clinical improvement or response) will be plotted by AP-SA02 and placebo at TOC for study drug (Day 12), TOC for BAT (7 days [ $\pm 1$  day] after the end of BAT) and EOS (28 days after the end of BAT) by both investigator and CEAC.

Microbiological outcome at Day 5, Day 7, TOC for study drug (Day 12), TOC for BAT, and EOS will be determined programmatically based on blood culture results tested by local microbiology laboratories per [Table 3](#) as 1 of the outcomes: Eradication, Presumed eradication, Persistence, Presumed persistence, Recurrence. The microbiological outcome at Day 5, Day 7, TOC for study drug (Day 12), TOC for BAT, and EOS will be summarized with counts and percentages of subjects based on categories in [Table 3](#).

The Chi-square test p-value will be provided for the counts of microbiological eradication (including presumed eradication) and microbiological persistence (including presumed persistence) compare AP-SA02 and placebo.

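### Estimate NEWS2, CRP and IL-10 differences by ANCOVA on baseline, and replace within-arm p-values, which cannot separate drug from background therapy and lean towards the larger active arm

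*SAP*

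**What the plan says.** SAP 3.4.1 summarises NEWS2 in hospital by study day, with change from baseline, and attaches two p-values. The first is within arm: "A paired t-test p-value will be used to compare the baseline value with each scheduled post-baseline values". The second is between arms: "An unpaired t-test p-value will be used for the change from baseline at each scheduled study day to compare AP-SA02 and placebo". SAP 3.6 repeats the pair for CRP and IL-10, and SAP 3.7.2 and 3.7.3 repeat it for laboratory tests and vital signs. Results are laid out by treatment group (SAP 3.4 and 3.6). No model in the SAP takes a baseline value as a covariate; the Cox models contain treatment alone.

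On size, SAP 2.2.4 states: "Phase 2a will have an initial sample size of approximately n = 42 with a study drug to placebo allocation of 2:1". The aim given there is 38 or more evaluable subjects.

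Two statements set the status of these tests. SAP 3.1.4 says there will be no formal testing. Protocol 9.2.1 calls for descriptive summaries by arm with 95% confidence intervals and plans no formal hypothesis tests. SAP section 6 does not list the t-tests as a departure from the protocol.

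**The concern.** Phase 2a inclusion criterion 7 requires at least one abnormal sign or symptom around randomisation, and all subjects receive best available therapy. NEWS2 and the inflammatory markers should therefore fall whether or not AP-SA02 works. A test against baseline within an arm asks whether subjects changed. It does not ask whether the drug changed them.

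The arms also differ in size, so the same true fall reaches p < 0.05 more often on active than on placebo. A table with a small p-value under AP-SA02 and a large one under placebo invites the reading that the drug worked. That pattern can arise with no drug effect at all.

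Separately, the between-arm comparison uses baseline only by subtraction. With about 13 evaluable placebo subjects, precision is scarce, and a regression on baseline would recover some of it from data already collected.

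**Working it through.** **The plan's own figure.** 42 × 0.90 = 37.8, or 38 evaluable subjects, which at 2:1 is about 25 active and 13 placebo. Exact one-sided Fisher power at 0.05 for 80% versus 30% response is 87.8% at 25:13 and 90.8% at 28:14. The stated power of at least 80% holds. It concerns clinical response at Day 12 and plays no part in what follows.

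**Within-arm tests.** Let d be the true mean change divided by the SD of the change. The documents give no value for d, so it is an assumption shown over a range. The paired t-test with n subjects is significant (two-sided 0.05) when the observed ratio exceeds t(0.975, n−1)/√n:

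- n = 25: 2.064/5 = 0.41
- n = 13: 2.179/3.606 = 0.60

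Power in each arm comes from the non-central t distribution with n−1 degrees of freedom and non-centrality d√n. With the same d in both arms and independent arms, P(active only) = P_A × (1 − P_P), and the reverse for placebo only.

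| d | P_A (n=25) | P_P (n=13) | Active only | Placebo only |
|---|---|---|---|---|
| 0.3 | 30.2% | 16.9% | 25% | 12% |
| 0.5 | 67.0% | 38.2% | 41% | 13% |
| 0.8 | 97.0% | 75.4% | 24% | 2% |
| 1.0 | 99.8% | 91.1% | 9% | 0.2% |

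For example, at d = 0.5: 0.670 × (1 − 0.382) = 0.414.

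**How much is due to 2:1 allocation.** Compare the 42 randomised subjects split 28:14 and 21:21, at d = 0.5:

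- 28:14: power 72.3% and 41.0%; active only 43%, placebo only 11%; discordant in 54%.
- 21:21: power 58.7% in each arm; 0.587 × 0.413 = 24% each way; discordant in 48%.

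Discordant pairs are therefore common even with equal arms. At this d, unequal allocation mainly tilts them towards active.

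**Between-arm test.** Let ρ be the correlation between baseline and follow-up, with equal SDs at both times (σ² = 1). Both are assumptions.

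- Change-score variance: 2(1 − ρ)
- ANCOVA residual variance: 1 − ρ²
- Ratio: (1 − ρ²)/[2(1 − ρ)] = (1 + ρ)/2

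| ρ | Ratio | Change-score N matching 38 with ANCOVA (38/ratio) |
|---|---|---|
| 0.3 | 0.65 | 58 |
| 0.5 | 0.75 | 51 |
| 0.7 | 0.85 | 45 |

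Chance imbalance matters too. The standard error of the baseline difference is √(1/25 + 1/13) = 0.34 SD. An imbalance of that size shifts the change-score difference by (1 − ρ) × 0.34, which is 0.24, 0.17 and 0.10 SD at the three correlations.

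**Validity.** In 40,000 simulated trials at 25:13 with no treatment effect and a common fall, the unpaired t-test on change rejected in 5.0% (ρ = 0.3) and 4.9% (ρ = 0.5). It keeps its error rate.

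**The case against.** The strongest reply is that nothing planned here is invalid. The direct between-arm comparison follows the within-arm test in the next sentence. Baseline enters it by subtraction, and its type I error is correct. The SAP nowhere says that the two within-arm p-values will be set against each other, and both documents disclaim formal testing. NEWS2 by day is one entry in a long, unranked list of endpoints. All of this stands, and it keeps the point at the level of an improvement.

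A reader might infer more than the documents support:

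- **That the SAP ignores baseline.** It does not. It subtracts baseline where a regression would use it more efficiently.
- **That a one-sided pattern of significance would be purely an allocation artefact.** Equal arms would still give 24% each way at d = 0.5.
- **That the misleading pattern is always frequent.** It peaks near d = 0.5. If subjects improve strongly on background therapy, it fades, to 9% active only at d = 1.0.
- **That the same harm applies to safety data.** For laboratory values and vital signs, flagging change more readily on active does not produce a false efficacy claim, so the argument does not carry over directly.

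It is also fair to say that ANCOVA by visit does not deal with discharge. NEWS2 is analysed only while subjects are in hospital, so later days describe those still admitted. A repeated-measures model with baseline as covariate would be an equally defensible choice, but it would not by itself settle that question either.

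**Conclusion.** The point holds as an improvement that needs no new data. For NEWS2, CRP and IL-10 the within-arm p-values carry no information about the drug that the between-arm comparison does not give better. If read side by side, they would mislead in AP-SA02's favour in roughly 9% to 41% of trials with no drug effect, for d between 0.3 and 1.0 at one visit and 25:13. Unequal allocation explains part of that, not all. The harm depends on that side-by-side reading, which a table laid out by arm invites but the SAP does not prescribe.

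The between-arm test is sound but uses the data less well than ANCOVA, which would cut residual variance by 35%, 25% or 15% at ρ of 0.3, 0.5 or 0.7. The values of d and ρ and the equal SDs are assumptions, since the documents give none of them. The expectation that both arms improve rests on the Phase 2a entry criteria and universal background therapy.

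**What to change.** In SAP 3.4.1 and 3.6:

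1. Replace the unpaired t-test on change with ANCOVA of the post-baseline value on treatment and baseline (as defined in SAP 3.1.2). Report the between-arm difference with its 95% CI. Use the log scale for CRP and IL-10 if the data are skewed.
2. Replace the within-arm paired p-values with mean change and 95% CI by arm. This agrees with protocol 9.2.1.
3. Record the change of method in SAP section 6.

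The same baseline adjustment can serve the between-arm comparisons in SAP 3.7.2 and 3.7.3. Removing the within-arm p-values there is optional.

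The cost is a few sentences of SAP text and simple reprogramming. It needs no new data, visits or subjects.
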